5.2 Participant Exclusion Criteria

An individual who meets any of the following criteria will be excluded from participation in this study:

- Grade IV esophagitis or gastric or duodenal ulcer
- Recent endoscopic esophageal variceal band ligation necessitating PPI therapy for prevention of banding ulcer
- Zollinger-Ellison syndrome
- Active Helicobacter pylori infection
- Pregnancy

5.3 Strategies for Recruitment and Retention

Potential patients will be identified by the Interventional Radiology (IR) clinical team at the time of referral for TIPS creation. At the time of referral for TIPS, patients will be screened for eligibility and exclusion criteria. Potential study candidates will be contacted by the IR team and the study will be described to the patient by the treating IR physician. Patients who are potentially interested in participating will then have the opportunity to undergo a formal written informed consent discussion at the time of the pre-TIPS IR clinic visit. No compensation will be provided for study participation.

5.4 Participant Withdrawal or Termination

5.4.1 Reasons for Withdrawal or Termination

An investigator may terminate participation in the study if:

- Any clinical AE, laboratory abnormality, or other medical condition or situation occurs such that continued participation in the study would not be in the best interest of the participant
- The participant meets an exclusion criterion (either newly developed or not previously recognized) that precludes further study participation.

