Precis: A total of 40 patients taking proton pump inhibitors (PPIs) who undergo transjugular intrahepatic portosystemic shunt (TIPS) creation as part of routine clinical care will be randomized in 1:1 fashion to either continue or discontinue their PPIs to determine whether these commonly used gastric acid suppressing agents increase risk of post-TIPS hepatic encephalopathy (HE). Patients will be assessed for symptoms of minimal HE (MHE), using the established psychometric hepatic encephalopathy score (PHES) battery of tests. MHE assessment will be conducted at two timepoints: at baseline prior to randomization and TIPS creation and approximately 4 weeks after randomization and TIPS creation. Stool samples will also be collected at both timepoints to allow characterization of the gastrointestinal (GI) tract microbiome using 16S rRNA sequencing. The pre to post-TIPS change in PHES scores will be compared between patients randomized to continue versus discontinue their PPIs. Quality of life (QOL) will also be assessed. Changes in the GI tract microbiome will be analyzed to determine whether this represents a potential biological mechanism linking PPI use with post-TIPS HE.

Objectives: The primary objective is to determine whether discontinuation of PPIs reduces the risk of post-TIPS HE. Additional secondary objectives will include a comparison of cirrhosis-specific and gastroesophageal reflux disease-specific QOL in the PPI continuation and discontinuation groups. An exploratory objective is to determine whether PPI induced changes in the GI tract microbiome represent a potential biological mechanism mediating PPI-induced risk of post-TIPS HE.

Endpoints: Change in PHES pre to post-TIPS by intention-to-treat (ITT) (primary endpoint). Per-protocol change in PHES; change in Chronic Liver Disease Questionnaire (CLDQ) and Quality of Life in Reflux and Dyspepsia (QOLRAD) scores pre to post-TIPS (secondary endpoints). Mediation analysis of GI tract bacterial taxon abundances as a potential link between PPI use and post-TIPS HE (exploratory endpoint).

Population: 40 male and female Duke University Hospital patients over the age of 18 taking PPIs and undergoing TIPS placement as part of routine clinical care

Phase: 2

[figure not shown]
Number of Sites Enrolling Participants: 1

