5.4.2 Handling of Participant Withdrawals or Termination

Patients who withdraw consent prior to randomization will not have undergone any study related intervention. Therefore, replacement of these participants will be permitted. Any patients who undergo randomization and withdraw prior to completion of the study will be analyzed according to the principle of ITT.

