7.3.5 Early Termination Visit

Not applicable.

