8.1.2 Definition of Serious Adverse Events (SAE)

An AE or suspected adverse reaction is considered “serious” if, in the view of the investigator, it results in any of the following outcomes: death, a life-threatening adverse event, prolongation of hospitalization, or a persistent or significant incapacity or substantial disruption of the ability to conduct normal life functions. Important medical events that may not result in death, be life-threatening, or result in prolongation of hospitalization may be considered serious when, based upon appropriate medical judgement, they may jeopardize the patient or subject and may require medical or surgical intervention to prevent one of the outcomes listed in this definition. Examples of such medical events include development of grade IV esophagitis, gastric or duodenal ulcers, or West-Haven grade 4 HE (e.g. comatose, unresponsive to pain, decorticate or decerebrate posturing).

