8.3 Time Period and Frequency for Event Assessment and Follow-Up

The occurrence of an AE or SAE may come to the attention of study personnel during the study or during routine clinical monitoring following completion of the study. All AEs not meeting the

criteria for SAEs will be captured on the CRF. Information to be collected includes event description, time of onset, clinician's assessment of severity, relationship to the study intervention (assessed only by those with the training and authority to make a diagnosis), and time of resolution/stabilization of the event. All AEs occurring while on study must be documented appropriately regardless of relationship. All AEs will be followed to adequate resolution.

Any medical condition that is present at the time that the participant is screened will be considered as baseline and not reported as an AE. However, if the study participant's condition deteriorates at any time during the study, it will be recorded as an AE. UPs will be recorded in the data collection system throughout the study.

Changes in the severity of an AE will be documented to allow an assessment of the duration of the event at each level of severity to be performed. AEs characterized as intermittent require documentation of onset and duration of each episode.

The PI will record all reportable events with start dates occurring any time after informed consent is obtained until 7 (for non-serious AEs) or 30 days (for SAEs) after the last day of study participation. Events will be followed for outcome information until resolution or stabilization.

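### Section 5.4.1 allows removal from the study after randomisation for conditions that are also example SAEs, with no provision for collecting the only post-TIPS PHES

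*Combined protocol and SAP*

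**What the plan says.** Section 5.4.1 begins "An investigator may terminate participation in the study if" and gives two grounds. The first is a clinical AE, laboratory abnormality or other situation that makes continuing contrary to the patient's interest. The second is "The participant meets an exclusion criterion (either newly developed or not previously recognized) that precludes further study participation". Neither is limited to the time before randomisation, and both end participation in the study, not only the assigned instruction.

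Section 5.2 lists "Grade IV esophagitis or gastric or duodenal ulcer" among the exclusion criteria. Section 8.1.2, defining SAEs, says: "Examples of such medical events include development of grade IV esophagitis, gastric or duodenal ulcers, or West-Haven grade 4 HE".

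On outcome timing, the Precis says "MHE assessment will be conducted at two timepoints": before randomisation, and about 4 weeks after TIPS. Section 7.3.4 and the schedule in 7.3.7 put the second PHES, CLDQ and QOLRAD at the final visit, about Day 42. The section headed "7.3.5 Early Termination Visit" is marked as not applicable.

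On analysis, Section 5.4.2 says: "Any patients who undergo randomization and withdraw prior to completion of the study will be analyzed according to the principle of ITT". Section 10.3 defines the ITT dataset as all randomised patients. Section 10.4.2 estimates each arm's mean from individual post-minus-pre PHES differences. No section says how a missing post-TIPS score is handled, and Section 10.4.5 plans no retention analysis.

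**The concern.** An eligibility rule is being used as a removal rule after randomisation, and some conditions that trigger it are outcomes the trial treats as harms. Randomisation is on Day 1 and the only post-treatment assessment is at about Day 42, so a patient can be removed at any time over roughly 41 days and leave no primary outcome.

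This missingness is created by the protocol, and it need not fall equally on the arms. Ulcer and severe esophagitis are plausibly linked to stopping acid suppression. The patient and treating physician know the assignment, and the PI, who directs safety oversight, also holds the randomisation codes (Sections 8.6 and 10.6.1). At stake is the comparability of the arms on PHES, CLDQ and QOLRAD in a trial with 20 patients per arm and no stated allowance for dropout.

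**Working it through.** **Step 1: what termination does to the primary outcome.**
- Section 5.4.1 ends participation, possibly after randomisation.
- Sections 7.3.4 and 7.3.7 provide one post-TIPS PHES, at about Day 42.
- Section 7.3.5 provides no visit at termination, and no other text keeps a terminated patient for the Day 42 assessment.
- Section 10.4.2 needs a post-TIPS score for each patient in the mean.

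With k patients terminated in an arm of 20, the estimator can be computed on 20 − k only. ITT decides who belongs in the analysis; it cannot supply a score that was never collected.

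**Step 2: could it differ by arm?** Section 2.3.1 reports, for discontinuation versus continuation in the cited deprescribing trial, heartburn of 54.8% vs 8.3% and endoscopic esophagitis of 69.6% vs 20.4%. These are not the exclusion-level events, so they show only that acid-related problems were more frequent after stopping. The same section reports no ulcers and no grade IV esophagitis in the discontinuation arm. That trial had excluded such patients at entry and was in patients aged 65 and older with a history of esophagitis, not in TIPS patients.

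**Step 3: loss of power.** Section 10.5 states 71% to 96% power with 20 per arm. It gives no SD, so the figure cannot be reproduced forward. Solving backward with a two-sided t-test at 0.05 gives standardised differences of 0.816 (71%) and 1.204 (96%); the normal approximation gives 0.795 and 1.173. Power was then recomputed with noncentrality d / √(1/20 + 1/(20 − k)) and 38 − k degrees of freedom:

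| Lost from discontinuation arm | Share of arm | Power, d = 0.816 | Power, d = 1.204 |
|---|---|---|---|
| 0 | 0% | 71.0% | 96.0% |
| 1 | 5% | 69.8% | 95.5% |
| 2 | 10% | 68.5% | 95.0% |
| 3 | 15% | 67.1% | 94.4% |

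**Step 4: possible shift in the arm mean.** If the k lost patients would have differed by g SD on average from those kept, the observed arm mean differs from the full-arm mean by (k/20) × g. The documents give neither the size nor the sign of g. For an assumed size of 0.5 to 1.5 SD, in either direction:
- k = 1: 0.025 to 0.075 SD
- k = 2: 0.05 to 0.15 SD
- k = 3: 0.075 to 0.225 SD

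**Step 5: how often?** No event rate is given for TIPS patients. With an assumed rate p, the chance of at least one such event among 20 patients is 1 − (1 − p)^20: 18% at p = 1%, 33% at 2% and 64% at 5%. The chance of two or more is 2%, 6% and 26%.

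**Step 6: the adverse event windows.** Section 7.3.3 records AEs within 30 days of TIPS, which is about Day 14 + 30 = Day 44. Section 8.3 counts 7 days (non-serious) or 30 days (SAEs) "after the last day of study participation", which for a completer is Day 42 + 7 = 49 and Day 42 + 30 = 72. The two clocks have different starting points, and only the second moves with termination. The protocol does not say which governs for a terminated patient.

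**The case against.** The strongest reply is that the rule is narrow and rarely used. It is discretionary, and the criterion must be one that precludes further participation. The cited trial reported no ulcers or grade IV esophagitis after stopping, no study endoscopy is scheduled, and Section 8.5 halts the intervention at three SAEs judged definitely or probably related to PPI discontinuation. All of this stands and limits the size of the point. It does not supply the missing score when the rule is used.

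A second reply is that Sections 5.4.2 and 10.3 keep every randomised patient in the ITT set, so this is only a missing-data question. It is right that no one is formally dropped from the set. But this missingness is avoidable at source, and an analysis method is a poorer remedy than collecting the score.

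Two stronger readings are tempting:
- A reader might infer that the rule biases the trial in favour of discontinuation on both benefit and harm. The documents do not support this. Nothing in them says that a patient with an ulcer or esophagitis would have a worse PHES. On harm, the AE endpoint in Section 10.4.3 counts patients with at least one AE, so the triggering event is already counted.
- A reader might infer that AE capture closes a week after termination. Section 7.3.3 sets a clock from TIPS without making it depend on participation, and Section 8.3 follows events to resolution or stabilisation. What remains is two unreconciled windows, not a demonstrated early cutoff.

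**Conclusion.** The point holds as a gap in outcome collection. The protocol permits removal after randomisation for conditions it also treats as example harms, and it has no route to the Day 42 assessments for a patient so removed. The ITT promise cannot be kept for that patient's PHES, CLDQ or QOLRAD, and the loss may differ by arm.

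The expected size is small. Each case is 5% of an arm, and one or two losses cost about 1 to 2.5 percentage points of power at the lower end of the stated range. The shifts in Step 4 and the probabilities in Step 5 rest on assumed values of g and p; they show scale and are not estimates. The direction of any PHES bias is unknown. The case for change is that the gap is certain from the text and nearly free to close.

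**What to change.** In Sections 5.4.1 and 7.3.5, separate ending the assigned study intervention from ending outcome collection:
- Limit removal from the study for an exclusion criterion to the time before randomisation.
- State that every randomised patient, including one whose intervention is ended under either ground of 5.4.1, is still assessed for PHES, CLDQ and QOLRAD at the routine 4-week post-TIPS visit unless consent is withdrawn. Put this in 7.3.5 in place of the not-applicable entry.
- State that decisions about PPI use and care remain with the investigator and treating physicians. The change concerns data collection only.
- Reconcile the AE windows in 7.3.3 and 8.3 so that one window applies to all randomised patients, whether or not the intervention was ended.

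The cost is a wording amendment to 5.4.1, 7.3.3, 7.3.5 and 8.3. No visit is added, because Section 7.1.2 already lists the 4-week follow-up as standard of care. The small downside is that some retained patients may be back on PPIs, which slightly dilutes the contrast between arms; an ITT comparison accepts this. With such patients assessed, this source of missing scores disappears and the planned 20 per arm is preserved against it. Scores missing for other reasons still need a stated method.

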5.4.2 Handling of Participant Withdrawals or Termination

Patients who withdraw consent prior to randomization will not have undergone any study related intervention. Therefore, replacement of these participants will be permitted. Any patients who undergo randomization and withdraw prior to completion of the study will be analyzed according to the principle of ITT.

5.5 Premature Termination or Suspension of Study

This study may be temporarily suspended or prematurely terminated if there is sufficient reasonable cause. If the study is prematurely terminated or suspended, the PI will promptly inform the IRB and will provide the reason(s) for the termination or suspension.

Circumstances that may warrant termination or suspension include, but are not limited to:

- Determination of unexpected, significant, or unacceptable risk to participants
- Demonstration of efficacy that would warrant stopping
- Insufficient compliance to protocol requirements
- Data that are not sufficiently complete and/or evaluable
- Determination of futility

Study may resume once concerns about safety, protocol compliance, data quality are addressed and satisfy the IRB.

6 Study Agent

Patients will be randomized to receive instructions to stop their existing PPI therapy (experimental/discontinuation/deprescribing arm) or to receive no specific instructions regarding PPI therapy (control/continuation arm). Therefore, considerations related to storage, handling, formulation, and labeling of study agent are not applicable.

7 Study Procedures and Schedule

7.1 Study Procedures/Evaluations

7.1.1 Study Specific Procedures

The following will study specific procedures will occur:

- Prior to randomization, all patients will undergo assessment of MHE, using the established PHES battery of pencil-and-paper tests (Figure 3), QOL assessments using the CLDQ and QOLRAD surveys, and will be provided with return-by-mail at home stool collection kits
- Patients will be randomized to either receive instructions to immediately discontinue their PPI, or to receive no specific instructions regarding their PPI
- Patients in the PPI discontinuation arm will receive intermittent phone call reminders encouraging them to refrain from PPI use, to attempt lifestyle interventions to counteract GERD symptoms (e.g. smoking cessation, avoiding late evening meals, and head-of-the-bed elevation) (40), and to use on-demand over-the-counter histamine H2 blocker therapy for intolerable GERD symptoms
- Approximately 4 weeks following TIPS creation, all patients will undergo reassessment of MHE and QOL and will be provided with return-by-mail at home stool collection kits
- At the completion of the study, all patients will be invited to resume or discontinue PPI therapy at their discretion and upon discussion with their primary care, gastroenterology, and IR physicians

Psychometric Hepatic Encephalopathy Score

Test	Description
Number connection test A (NCT-A)	Randomly dispersed numbers are to be connected with each other in serial order as quickly as possible.
Number connection test A (NCT-B)	Randomly dispersed numbers and letters are to be connected in alternating series (1-A-2-B...) as quickly as possible.
Digit-symbol	Digits from 1 to 9 are assigned respective symbols. Under each digit the corresponding symbol is to be written within a given time.
Serial dotting	Draw a dot inside each circle as quickly as possible.
Line tracing	A given line is to be traced as quickly as possible.

Figure 3: PHES tests from (41).

7.1.2 Standard of Care Study Procedures

The following occur as standard of care for all patients undergoing TIPS creation:

- After receiving a referral TIPS creation, the treating IR physician reviews the patient's electronic medical records including history, medications, allergies, physical examination and imaging findings, and laboratory tests to evaluate the patient's candidacy for the procedure
- All patients referred for TIPS creation undergo a pre procedure consultation with the treating IR physician
- All TIPS procedures are performed under general anesthesia. Portal vein access is achieved using intracardiac echocardiography/intravascular ultrasound guidance. Controlled expansion covered Viatorr covered stent grafts are deployed and dilated to achieve a target reduction in the portosystemic pressure gradient of 50% or <12 mm Hg for varices and <8 mm Hg for ascites (1). Patients are admitted to the hospital following TIPS creation for post procedure observation.
- Patients undergo routine follow up with the IR clinical team approximately 4 weeks after TIPS creation.

7.2 Laboratory Procedures/Evaluations

7.2.1 Clinical Laboratory Evaluations

Routine clinical laboratory evaluation prior to TIPS procedure includes assessment of a complete metabolic panel, complete blood count, and coagulation studies (prothrombin time/international normalized ratio). These laboratory evaluations are performed as part of standard of care for patients undergoing TIPS creation. No study specific clinical laboratory assessments are proposed.

7.2.2 Other Assays or Procedures

Microbiome analyses from stool samples will be performed by Duke University core facilities according to established protocols. DNA extraction will be performed using the Qiagen PowerSoilPro DNA Kit. Polymerase chain reaction amplification of the V4 variable region of the 16S rRNA gene will be performed following the Earth Microbiome Project protocol (<http://www.earthmicrobiome.org/>). DNA sequencing will be performed by the Duke Sequencing and Genomic Technologies shared resource on an Illumina MiSeq instrument. Sequence data will be analyzed by the Genomic Analysis & Bioinformatics Core.

7.2.3 Specimen Preparation, Handling, and Storage

Patients will be provided with commercially available at home stool DNA Genotek OMNIgene-GUT collection kits (<https://www.dnagenotek.com/US/products/collection-microbiome/omnigene-gut-kit/OMR-200.100.html>). Patient friendly instructions for use of this kit are available from the manufacturer and will be further explained to study participants by the CRC. Briefly, at home after stooling, patients use a small spatula provided in the kit to obtain a stool sample which is placed in a stabilizing collection tube. The tube is then placed in a bio-specimen bag. Fecal samples collected with the OMNIgene-GUT kit can be stored at room temperature for up to 60 days.

7.2.3 Specimen Shipment

Patients will be supplied with a prepaid 2-way mailers shipping box with peelable adhesive strip for sample return. Custom labels are created for traceability.

7.3 Study Schedule

7.3.1 Screening

Patients referred to IR for TIPS creation are screened for procedure candidacy by the treating IR physician. At this time screening for study eligibility will also be performed. Patients deemed eligible for the study will be contacted by the IR clinical team to confirm ongoing PPI use and to introduce them to the study prior to the routine pre-TIPS IR clinic visit. Patients potentially interested in study participation will then be referred to the study team CRC. The CRC will then formally screen the patient for eligibility based on a review of the electronic medical record. In accordance with IRB and HIPAA regulations, no PHI will be recorded during this screening evaluation.

7.3.2 Enrollment/Baseline

At the time of the routine pre-TIPS IR clinic visit, patients who remain potentially interested in participating in the study will meet with the study team CRC and informed written consent will be obtained from subjects who elect to participate. Baseline MHE assessment via the PHES tests and QOL surveys will then be administered and home stool collection kits will be provided.

7.3.3 Follow-Up

After enrollment and baseline assessments, open-label randomization will be performed. Patients randomized to the PPI discontinuation arm will be contacted via telephone and instructed to discontinue their PPI. These patients will receive a reminder telephone call approximately 1 week later. All patients will then undergo the TIPS procedure per routine standard of care. While inpatient after the TIPS procedure and 2 weeks later by telephone, patients in the PPI discontinuation arm will again be reminded to abstain from PPI use. Adverse events occurring within 30 days of TIPS creation will be recorded, in accordance with Society of Interventional Radiology guidelines (42).

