4.1 Description of the Study Design

The proposed study is a single center randomized, open-label, deprescribing trial of PPI users undergoing TIPS creation. The study will involve two arms: the experimental/PPI discontinuation arm will be instructed to stop taking their PPIs prior to TIPS creation and the control/PPI continuation arm will receive no special instructions regarding their preexisting PPI medication. Patients will be assessed for MHE using the PHES test battery and for QOL using the CLDQ and QOLRAD surveys prior to randomization, and approximately 6-8 weeks later after TIPS creation. Stool samples will be collected at both time points. After the second and final assessment approximately 4 weeks after TIPS creation patients will have completed the study.

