7.3.7 Schedule of Events Table

Procedures	Referral for TIPS (~Day -14)	Pre-TIPS IR clinic visit (Day 0)	Post-clinic phone call (Day 1)	PPI reminder phone call (~Day 7)	TIPS performed (~Day 14)	In person PPI reminder (Day 15)	PPI reminder phone call (~Day 28)	Post-TIPS IR clinic visit (~Day 42)
Screening by IR clinical team	X							
Informed written consent		X						
MHE assessment		X						X
QOL assessment		X						X
Stool sample		X						X

collection kit provided								
Randomization			X					
Reminder to refrain from PPI use				X		X	X	
TIPS procedure					X			

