10.4.3 Analysis of the Secondary and Exploratory Endpoints

- Per-protocol evaluation of PPI deprescribing on post-TIPS HE: Statistical analysis will be conducted via a two-sided unpaired T-test of the hypothesis $H_0: \mu_{+PPI} = \mu_{-PPI}$ versus $H_1: \mu_{+PPI} \neq \mu_{-PPI}$. Here μ_{+PPI} and μ_{-PPI} are the pre to post-TIPS change in PHES estimated from the sample means in the per-protocol dataset.
- ITT analysis of the change in CLDQ and QOLRAD scores: Statistical analysis will be conducted via a two-sided unpaired T-test of the hypothesis $H_0: \mu_{+PPI} = \mu_{-PPI}$ versus $H_1: \mu_{+PPI} \neq \mu_{-PPI}$. Here μ_{+PPI} and μ_{-PPI} are the pre to post-TIPS change in QOL scores on the respective surveys, estimated in the ITT dataset.
- Episodes of overt HE: Statistical analysis will be conducted via a two-sided Fisher's exact test of the hypothesis $H_0: p_{+PPI} = p_{-PPI}$ versus $H_1: p_{+PPI} \neq p_{-PPI}$. Here p_{+PPI} is the proportion of patients in the PPI continuation arm experiencing at least one episode of

greater than or equal to West-Haven grade 2 overt HE, and p_{+PPI} is the corresponding proportion in the PPI discontinuation arm.

- On-demand requirement for acid suppression therapy: The proportion of patients in the PPI discontinuation arm needing on-demand histamine H2 blockers and PPIs will be reported.
- Adverse events: Statistical analysis will be conducted via a two-sided Fisher's exact test of the hypothesis $H_0: p_{+PPI} = p_{-PPI}$ versus $H_1: p_{+PPI} \neq p_{-PPI}$. Here p_{+PPI} is the proportion of patients in the PPI continuation arm experiencing at least AE, and p_{-PPI} is the corresponding proportion in the PPI discontinuation arm.
- Exploratory analysis of the role of the GI tract microbiome in mediating PPI induced post-TIPS HE: Analysis will be conducted using statistical mediation analysis (34, 43). Criteria for assessing mediation are based on the following equations:

$$Y = \mu_1 + c X + \varepsilon_1$$

$$M_j = \mu_2 + a X + \varepsilon_2$$

$$Y = \mu_3 + c' X + b M_j + \varepsilon_3$$

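### Only the discontinuation arm has scheduled study contacts between baseline and the final visit, and no step asks both arms about AEs, overt HE or drug use, so opportunity for detection is unequal

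*Combined protocol and SAP*

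**What the plan says.** Section 7.3.3 (Follow-Up) sets out the contacts after baseline. "Patients randomized to the PPI discontinuation arm will be contacted via telephone and instructed to discontinue their PPI"; the Schedule of Events (7.3.7) puts this call on Day 1. "These patients will receive a reminder telephone call approximately 1 week later", about Day 7. Two further contacts follow TIPS, one at the bedside during the admission and one call a fortnight afterwards. At both, "patients in the PPI discontinuation arm will again be reminded to abstain from PPI use"; the schedule shows these on Day 15 and about Day 28. The schedule row is labelled "Reminder to refrain from PPI use". Section 7.1.1 adds that the discontinuation arm's telephone reminders also encourage lifestyle measures against reflux and H2 blockers for intolerable symptoms.

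For the other arm, section 4.1 says that "the control/PPI continuation arm will receive no special instructions regarding their preexisting PPI medication". No study contact is specified for it between Day 0 and about Day 42.

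On detection, section 8.3 says that an AE "may come to the attention of study personnel during the study or during routine clinical monitoring" after the study ends, and requires every on-study AE to be documented. The schedule has no row for AE enquiry, West-Haven grading or medication use. Section 7.3.4 lists only minimal HE, quality of life and stool kits for the final visit.

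Sections 10.2 and 10.4.3 nevertheless test AEs and overt HE between arms by two-sided Fisher's exact test, each scored as at least one event per patient. For acid suppression, section 10.4.3 says: "The proportion of patients in the PPI discontinuation arm needing on-demand histamine H2 blockers and PPIs will be reported".

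**The concern.** A patient who mentions heartburn or a confused day on a reminder call has told study staff, and section 8.3 then requires the event to be recorded. A control with the same symptom at home has no matching route. Because each patient is scored as having any event or none, a single mild report can change that patient's status.

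The consequence falls on the trade-off that section 2.2 gives as a reason for the trial: whether reflux harm after stopping a PPI outweighs any reduction in HE. Extra detection on discontinuation would make harm look larger and any fall in overt HE look smaller.

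The drug-use gap is separate and needs no assumption about what is said on calls. If use is reported for one arm, the reader cannot see how many controls stopped or reduced their PPI, and so cannot judge the contrast actually achieved.

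**Working it through.** The plan gives no figure for detection, so there is none to reproduce. The check has two parts.

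**1. Count the scheduled contacts (7.1.1, 7.1.2, 7.3.3, 7.3.4, 7.3.7).**

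| Time | Discontinuation | Control | Shared clinical contact |
|---|---|---|---|
| Day 1 call | yes | none stated | no |
| ~Day 7 call | yes | none | no |
| Day 15 inpatient reminder | yes | none | yes, both arms admitted after TIPS |
| ~Day 28 call | yes | none | no |
| ~Day 42 visit | yes | yes | yes |

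Between Day 0 and about Day 42 the count is 4 v 0. The schedule's Day 1 column carries no arm label; if controls were also telephoned then, it would be 4 v 1. The Day 1 and Day 7 calls precede TIPS (about Day 14), so they cannot detect post-TIPS overt HE. The Day 15 reminder falls when both arms are under observation. For overt HE after TIPS, the contact that clearly differs is the Day 28 call: 1 v 0.

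For AEs the count depends on the window. Section 7.3.3 records AEs within 30 days of TIPS, and section 8.3 records from consent to 7 days (non-serious) or 30 days (serious) after participation ends. Under the second, events mentioned on the Day 7 call count. Under the first, read as the 30 days after TIPS, they do not.

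**2. What unequal detection would do to the Fisher test.**

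Inputs: 20 patients per arm (10.5); two-sided p below 0.05 (10.4.1). The true AE rate (50% in both arms) and the detection probabilities are assumptions.

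Observed rate = true rate × detection probability. The rejection probability is the sum, over all pairs (a, b) from 0 to 20 whose Fisher p is below 0.05, of Bin(a; 20, observed rate on discontinuation) × Bin(b; 20, observed rate in controls).

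| Detection, control v discontinuation | Observed rates | False-positive rate |
|---|---|---|
| 90% v 90% | 45% v 45% | 2.2% |
| 80% v 90% | 0.5 × 0.8 = 40% v 0.5 × 0.9 = 45% | 2.9% |
| 70% v 90% | 35% v 45% | 5.4% |
| 60% v 85% | 30% v 42.5% | 7.8% |
| 50% v 90% | 25% v 45% | 17.9% |

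Fisher's test is conservative at this size, which is why the equal-detection row is near 2% and not 5%. At the wider gaps, nearly all false positives show excess events on discontinuation (17.89 of 17.91 percentage points in the last row).

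For overt HE, assume true rates of 60% in controls and 30% on discontinuation (section 2.1 gives 30% to 60% for post-TIPS HE), with full detection on discontinuation. Power is 34.7% if all control cases are found, 22.7% if 10% are missed (observed 54% v 30%) and 13.6% if 20% are missed (48% v 30%). These miss rates are also assumptions; with one differing call, the true figure could be near zero.

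**The case against.** The contacts are described as instructions and reminders, not as AE or HE enquiries. Both arms are admitted after TIPS, attend the four-week visit and may have unscheduled visits (7.3.6). The medical record is source data for every patient (section 11). Overt HE of West-Haven grade 2 or above, with signs such as gross disorientation, is conspicuous and need not depend on a reminder call to be found. Section 8.3 describes how events may surface; it does not say that only noticed events count. All of this stands. A reader might infer that AE and overt-HE data will in fact be collected unequally. The documents show only unequal opportunity.

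A reader might also infer that acid-suppressant use in controls goes unrecorded. That is too strong: sections 7.5 and 11 do not expressly limit collection on the case report form (CRF) to one arm. What is explicit is one-arm reporting. In addition, section 11 lists on-demand use but not the regular daily PPI dose, which the per-protocol definition in section 10.3 needs for patients who continued.

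The direction is likely rather than certain. Patients and treating physicians are unblinded (10.6.1), and a physician who suspects that PPIs cause HE could look harder in controls.

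The objection does not supply a common enquiry. No scheduled step puts the same questions to both arms, and the stated assessor blind covers only PHES and quality of life.

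**Conclusion.** The point holds as unequal opportunity for detection, chiefly for mild AEs, together with one-arm reporting of acid suppression. For post-TIPS overt HE it rests mainly on one call. The likely effect is against discontinuation.

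Its size cannot be stated, because the documents give no detection rates. A 10-point detection gap moves the false-positive rate only from about 2% to 2.9%; a 20-point gap brings it to 5.4%, about the nominal level. The 17.9% figure needs a 40-point gap, and nothing in the documents supports a gap that wide, so it should be read as an upper illustration and not as an expectation.

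A reader might extend the concern to the primary endpoint. The documents do not support that: PHES is scheduled at the same two visits in both arms, with a blinded assessor. The affected analyses are secondary, and the change is worth making because it is cheap and removes a plausible bias.

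**What to change.** 1. At the existing Day 42 visit, put one structured question set to both arms: AEs, overt-HE symptoms or episodes, daily PPI dose, and on-demand PPI and H2-blocker use. Add matching rows to the schedule and the CRF. Ask it after PHES and quality of life are complete, so that the answers do not unmask the coordinator beforehand.
2. Base the between-arm Fisher tests on that question set plus the same medical-record review in both arms. List events learned only from reminder calls separately, for safety. Reconcile the AE windows in 7.3.3 and 8.3 so that the tests have one counting period.
3. Report PPI and H2-blocker use for both arms in 10.2 and 10.4.3. The per-protocol set in 10.3 needs the same data.

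The cost is a short questionnaire and a record review for 40 patients by existing staff, and some recall error for mild events. Sample size, alpha and the primary analysis do not change. Extra control-arm calls are not needed, and they could influence PPI use in an arm meant to receive no specific instructions.
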